13.3 Treatment Re-Initiation

For subjects (Who achieve a confirmed CR on Avelumab and subsequently develop PD after stopping therapy; Who under disease progression due to brain metastasis; Who under disease progression mainly due to a metastatic lesion (nodal or visceral)) will be treated as EOT, but can reinitiate Avelumab therapy if the relevant criteria are met, per investigator and medical monitor decision. Treatment re-initiation and discontinuation after re-initiation will be tabulated and presented in the subject disposition.

[figure not shown]
For subjects who ever achieved CR, also defined as retreated subjects according to protocol, sparse PK and ADA blood samples will be collected according to the schedule as indicated in protocol Table 1-5. However, for subjects who under disease progression due to brain metastasis or a metastatic lesion (nodal or visceral), PK and ADA blood samples will be collected according to the schedule as indicated in protocol Table 1-3(Table 1-4), or Table 1-5.

CCI

[figure not shown]

CCI

CCI

[figure not shown]
CCI

CCI

CCI

15 Safety Analyses

Safety analyses will be done on the safety analysis set and according to the as-treated principle.

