Draft 0.3	11MAY2018	PPD	Modified per sponsor's comments received on 26MAR2018 and 10MAY2018.
Draft 0.4	29MAY2018	PPD	Modified per sponsor's comments received on 21MAY2018 and 24MAY2018.
Final 1.0	01JUN2018	PPD	Modified per sponsor's comments received on 25MAY2018 and 31MAY2018.
Final 2.0	13AUG2019	PPD	
 1. Add appendix of irAE and IRR 2. Add appendix of Toxicities for Laboratory Evaluations 3. Modify Section 12.2 Medications 4. Clarify ADA in secondary endpoint. 5. Add rule for incomplete date of prior/concomitant medication. 6. Modify definition of re-initiation

4 Purpose of the Integrated Analysis Plan

The purpose of this IAP is to document technical and detailed specifications for the final analysis of data collected for protocol MS100070-0035.

Results of the analyses described in this IAP will be included in the Clinical Study Report (CSR). Additionally, the planned analyses identified in this IAP will be included in regulatory submissions or future manuscripts. Any post-hoc, or unplanned analyses performed to provide results for inclusion in the CSR but not identified in this prospective IAP will be clearly identified in the CSR.

The IAP is based upon section 8 (Statistics) of the trial protocol and protocol amendments and is prepared in compliance with ICH E9.

5 Objectives and Endpoints

	Objective	Endpoint	IAP section
Primary Objective	
 • To evaluate the maximum tolerated dose (MTD) of avelumab (MSB0010718C) monotherapy in Chinese subjects. • To characterize the pharmacokinetics (PK) of avelumab in Chinese subjects. 	
Primary Endpoint
 
 • Occurrence of DLTs during the DLT observation period (first 21 days of treatment; excluding 10 mg/kg once weekly cohort). • PK profiles in Chinese subjects. 	
15
 
16.1
 
16.2

Secondary Objective	
 To determine the safety and tolerability of avelumab by assessing treatment-emergent adverse events (TEAEs) and treatment-related AEs for all dose groups according to the NCI-Common Terminology Criteria for Adverse Events (CTCAE) v4.03. To characterize immunogenicity of avelumab in Chinese subjects. 	Secondary Endpoint 
 Occurrence of TEAEs for all dose groups according to NCI-CTCAE v4.03. Occurrence of treatment-related AEs for all dose groups according to NCI-CTCAE v4.03. Serum titers of ADA against avelumab. 	14 15

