13.2 Exposure to Study Drug

The extent of exposure for avelumab will be characterized by duration (weeks), number of administrations, cumulative dose (mg/kg), dose intensity (mg/kg/cycle), relative dose intensity, number of dose delays.

Descriptive statistics will be used to summarize treatment exposure, based on the data being collected in “AVELUMAB ADMINISTRATION DETAILS” page of eCRF. Summaries will be performed on the safety analysis set. Subjects will receive an IV infusion of avelumab (over 1 hour

[- 10 minutes/+ 20 minutes, i.e., 50 to 80 minutes]) once every 2 weeks or, if 20 mg/kg once every 2 weeks have been established, 10 mg/kg every week for the first 12 weeks and once every 2 weeks thereafter starting at Week 13.

Safety analyses will be performed on the Safety Analysis Set. The safety endpoints will be tabulated by dose level and cohort, using descriptive statistics.

(1) Avelumab (3, 10, 20 mg/kg) once every 2 weeks (Q2W):

- **The duration of avelumab (weeks)** during the study is defined as:

$$\left(\frac{\text{date of last dose of avelumab} - \text{date of first dose of avelumab} + 14}{7} \right)$$

- **The cumulative actual treatment dose (mg/kg)** of avelumab per subject is the sum of the calculated actual dose levels of avelumab that the subject received (i.e. total dose administered (mg/kg)).
- **The dose intensity of avelumab (mg/kg/cycle)** per subject is defined as:

$$\left(\frac{\text{Cumulative dose of avelumab}}{0.5 * [(\text{date of last dose of avelumab} - \text{date of first dose of avelumab} + 14) / 7]} \right)$$

- **Total number of infusions received (n)**
- **Relative dose intensity of therapy (%):** The relative dose intensity per cycle is defined as $100 \times \text{actual dose intensity per cycle (mg/kg/cycle)} / (\text{planned dose level per cycle (mg/kg/cycle)})$

(2) Avelumab (10 mg/kg) once weekly (Q1W) for 12 consecutive weeks and then starting at Week 13, once every 2 weeks (Q2W):

- **The duration of avelumab (weeks) for first 12 weeks receiving Q1W dose per subject** is defined as:

$$\left(\frac{\text{Date of last dose of avelumab(Q1W)} - \text{date of first dose of avelumab(Q1W)} + 7}{7} \right)$$

- **The duration of avelumab (weeks) for subsequent weeks receiving Q2W dose per subject** is defined as:

$$\left(\frac{\text{Date of last dose of avelumab(Q2W)} - \text{date of first dose of avelumab(Q2W)} + 14}{7} \right)$$

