- **The cumulative actual treatment dose (mg/kg) of avelumab receiving Q1W dose** per subject is the sum of the calculated actual dose levels of avelumab that the subject received of Q1W dose (i.e. total Q1W dose administered (mg/kg)).
- **The cumulative actual treatment dose (mg/kg) of avelumab receiving Q2W dose** per subject is the sum of the calculated actual dose levels of avelumab that the subject received of Q2W dose (i.e. total Q2W dose administered (mg/kg)).
- **The dose intensity of avelumab (mg/kg/cycle) for first 12 weeks receiving Q1W dose per subject** is defined as:

$$\left(\frac{\text{Cumulative dose of avelumab (Q1W)}}{(\text{date of last dose of avelumab(Q1W)} - \text{date of first dose of avelumab(Q1W)} + 7) / 7} \right)$$

- **The dose intensity of avelumab (mg/kg/cycle) for subsequent weeks receiving Q2W dose per subject** is defined as:

$$\left(\frac{\text{Cumulative dose of avelumab (Q2W)}}{0.5 * [(\text{date of last dose of avelumab(Q2W)} - \text{date of first dose of avelumab(Q2W)} + 14) / 7]} \right)$$

- **Total number of infusions received (n) for Q1W dose and Q2W dose, respectively**
- **Relative dose intensity of therapy (%) for Q1W dose:** The relative dose intensity per cycle is defined as $100 \times \text{actual dose intensity per cycle (mg/kg/cycle) for Q1W dose} / (\text{planned dose level per cycle (mg/kg/cycle) for Q1W dose}$
- **Relative dose intensity of therapy (%) for Q2W dose:** The relative dose intensity per cycle is defined as $100 \times \text{actual dose intensity per cycle (mg/kg/cycle) for Q2W} / (\text{planned dose level per cycle (mg/kg/cycle) for Q2W dose}$.

Dose reduction is not allowed per protocol and will not be summarized.

Per protocol, Avelumab will be administered as 1-hour intravenous infusion. Subjects will receive the trial treatment once every 2 weeks (excluding 10 mg/kg once weekly cohort). Dose delays will be grouped into the following categories based on the deviation of the actual to the planned treatment administration day (relative to the previous non-zero dose date): no delay (including 1-2 days delays), 3-6 days delay, 7 or more days delay. For example, if one subject receives the study drug on day 1, then the next study drug administration date will be on day 15; however, if the

subject receives the study drug at day 16 or 17, this is considered as ‘no delay’. Any zero dose prior to the last treatment administration is considered as a dose interruption.

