15.2 Adverse Events (AE)

An AE is any untoward medical occurrence in a subject or clinical investigation subject administered a pharmaceutical product, which does not necessarily have a causal relationship with this treatment. An AE can therefore be any unfavorable and unintended sign (including an abnormal laboratory finding), symptom, or disease temporally associated with the use of a medicinal product, whether or not considered related to the medicinal product.

If the severity/intensity of a particular AE is not specifically graded by the guidance document, the Investigator is instructed to revert to the general definitions of Grade 1 through Grade 5 and use his or her best medical judgment.

The 5 general grades are:

- Grade 1: Mild
- Grade 2: Moderate
- Grade 3: Severe
- Grade 4: Life-threatening or disabling
- Grade 5: Death related to AE

AEs will be coded using the latest version of Medical Dictionary for Regulatory Activities (MedDRA). The severity of AEs will be graded by the investigator using the NCI-CTCAE version 4.03.

Treatment emergent adverse events (TEAEs) are those events that emerge during treatment having been absent pre-treatment, or worsen relative to the pre-treatment state and with onset dates

occurring within the first dosing day of study dose levels until 30 days after the last dose of study treatment.

All analyses described **Error! Reference source not found.** will be based on TEAEs (started during the on-treatment period) if not otherwise specified. The AE listings will include all AEs (whether treatment-emergent or not). AEs outside the on-treatment period will be flagged in the listings. A separate listing including AEs started after the on-treatment period will also be provided.

- **Related Adverse Events:** adverse events with relationship to study treatment (as recorded on the AE eCRF page, Relationship with study treatment = Related) reported by the investigator and those of unknown relationship (i.e. no answer to the question “Relationship with study treatment”).
- **Serious Adverse Events (SAE):** serious adverse events (as recorded on the AE eCRF page, Serious Adverse Event = Yes).
- **Related SAEs**
- **Adverse Events Leading to Treatment Discontinuation:** adverse events leading to permanent discontinuation of study treatment (as recorded on the AE eCRF page, Action taken with study treatment = Drug withdrawn).
- **Related AE Leading to Treatment Discontinuation**

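### Duration, dose intensity and dose-delay category for re-initiated subjects run across the off-treatment gap that SAP 13.3 calls end of treatment

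*SAP*

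**What the plan says.** SAP 13.3 (Treatment Re-Initiation) names three routes back to avelumab: progression after stopping in a subject with confirmed complete response, the brain route ("Who under disease progression due to brain metastasis"), and progression mainly from a nodal or visceral lesion. Subjects on any route "will be treated as EOT, but can reinitiate Avelumab therapy if the relevant criteria are met, per investigator and medical monitor decision". For them the section then specifies a disposition tabulation and the PK and ADA sampling schedule. It gives no rule for exposure or safety summaries.

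SAP 13.2 (Exposure to Study Drug) defines duration in the two-weekly cohorts as last dose date minus first dose date plus 14 days, in weeks. Dose intensity divides cumulative dose by half that span, and RDI divides dose intensity by the planned dose per cycle. The weekly cohort uses the same first-to-last form within its weekly part and within its two-weekly part. No formula has a term for a gap. Each dose delay is measured from the previous non-zero dose, and the subject is classified by the longest one; the top category is seven days or more.

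SAP 15.2 defines treatment-emergent events in one window per subject, from the first dosing day "until 30 days after the last dose of study treatment". The protocol's on-treatment period (8.5.3.1) is also one window, cut short only by a subsequent anticancer drug. Local surgery or radiotherapy would not trigger that cut.

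**The concern.** The SAP gives one interval two meanings. In disposition the subject has ended treatment and later restarted. In the exposure tables the same weeks are treatment time with doses missing. A subject who completed treatment after a complete response, and was later retreated on schedule, would be reported with a long exposure, a poor RDI and a long dose delay, although no dose was missed in either course.

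The safety window has a similar defect. Once the gap is longer than about 30 days, the single TEAE window takes in days that a per-course window would leave out. Under protocol 7.4.1.3, AE collection narrows after the 30-day visit to serious events and related nonserious events until day 90; after that only related serious events must be reported. The window then mixes time with full ascertainment and time with reduced ascertainment. The worst-grade laboratory summaries (SAP 15.3) and the worst ECOG status (SAP 15.5.2) also use the on-treatment period.

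TEAEs are a secondary endpoint, and cohorts are planned at 3 or 6 subjects, so one re-initiated subject can show in a cohort summary.

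**Working it through.** The plan states no figure here, so I applied the SAP 13.2 formulas literally to hypothetical subjects.

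**Inputs.** From the SAP: duration = (last dose − first dose + 14)/7 weeks; dose intensity (DI) = cumulative dose/(0.5 × duration); RDI = 100 × DI/planned dose; TEAE window = first dose to last dose + 30 days, counted inclusively. My assumptions: course lengths, gap lengths, a dose of 10 mg/kg every 2 weeks, and every dose on schedule within its course. Protocol 6.2 gives only minimum intervals after local treatment, not gap lengths. The gap is measured from the last dose of course 1 to the first dose of course 2. Day 0 is the first dose.

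**Check without a gap.** For 13 doses the last is on day 168: (168 + 14)/7 = 26 weeks; DI = 130/13 = 10; RDI = 100%. The formulas behave as intended.

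**26 + 6 doses, 26-week gap (182 days).**
- Course 1 ends on day 350, restart is on day 532, last dose on day 602.
- As written: (602 + 14)/7 = 88 weeks; DI = 320/44 = 7.27; RDI = 72.7%.
- Per course: 52 + 12 = 64 weeks; DI = 320/32 = 10; RDI = 100%.
- TEAE window: 602 + 31 = 633 days as written. Per course: (350 + 31) + (70 + 31) = 482. The excess is 151 days, namely days 31 to 181 of the gap: 60 days with reduced AE collection (days 31 to 90) and 91 after it.

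**6 + 6 doses, 8-week gap (56 days).**
- Course 1 ends on day 70, restart is on day 126, last dose on day 196.
- As written: (196 + 14)/7 = 30 weeks; DI = 120/15 = 8; RDI = 80.0%.
- Per course: 12 + 12 = 24 weeks; RDI = 100%.
- TEAE window: 227 days against 101 + 101 = 202. The excess is 25 days.

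**Other gap lengths.** Per-course RDI is 100% in every row.

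| Doses | Gap (weeks) | Weeks as written | Weeks per course | RDI as written | Extra TEAE days |
|---|---|---|---|---|---|
| 26 + 6 | 12 | 74 | 64 | 86.5% | 53 |
| 26 + 6 | 52 | 114 | 64 | 56.1% | 333 |
| 3 + 3 | 4 | 14 | 12 | 85.7% | 0 |
| 6 + 6 | 6 | 28 | 24 | 85.7% | 11 |
| 6 + 6 | 12 | 34 | 24 | 70.6% | 53 |

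If the gap is instead counted from 14 days after the last dose, the span grows by two weeks. The two main cases become 90 weeks with RDI 320/45/10 = 71.1%, and 32 weeks with RDI 120/16/10 = 75.0%.

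**Cohort mean RDI, six subjects, the other five at 100%.** (500 + 72.7)/6 = 95.5% and (500 + 80.0)/6 = 96.7%, so the mean falls by 4.5 and 3.3 points.

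**Weekly cohort.** Take 12 weekly and 20 two-weekly doses, a 26-week gap, then 6 doses. Protocol 6.2 has retreatment after complete response at the same dose and schedule, but SAP 13.2 does not say to which part the restart doses belong. Coded as weekly, the weekly-part span is 82 weeks and RDI is 180/82/10 = 22.0%. Coded as two-weekly, that part spans 76 weeks and RDI is 260/38/10 = 68.4%.

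**The case against.** Part of this is convention. RDI is meant to fall when doses are missed, and for the brain, nodal and visceral routes protocol 6.2 speaks of subjects continuing avelumab after local treatment. On that reading the interval is an interruption and a lower RDI is defensible. This stands as far as it goes, but it conflicts with the end-of-treatment label in SAP 13.3. It also does not cover retreatment after complete response, where treatment had stopped.

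A reader might infer that adverse events of surgery or radiotherapy in the gap become avelumab events. The documents do not support that. Days 0 to 30 after the last pre-gap dose are on-treatment under either method. Beyond that, unrelated nonserious events are mostly not collected. Treatment-emergent status is not attribution, and related events are tabulated separately. What remains is mainly serious events in days 31 to 90.

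A reader might also infer from the modification log that version 2.0 widened the definition. The log says only "Modify definition of re-initiation", version 1.0 is not available, and the protocol already speaks of re-initiation after brain metastasis. Only the three routes in the current text can be relied on.

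The consequences are also limited. DLTs (first 21 days) and the Day 1 PK parameters are untouched. The dosing listing shows days since the previous administration, and disposition counts re-initiations, so an affected subject can be identified. SAP section 14 is redacted, but the sections where exposure and TEAE rules belong are visible.

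**Conclusion.** The point holds as a minor inconsistency. As written, the SAP counts the interval between courses as exposure and as a dose delay for subjects whom it also classes as having ended treatment. In the two main cases duration is overstated by 24 weeks (88 against 64) and 6 weeks (30 against 24), and RDI falls from 100% to 72.7% and 80.0%. One such subject lowers a six-subject cohort mean by about 3 to 5 points. Any gap longer than one cycle affects duration and RDI; the TEAE window is affected only beyond day 30 of the gap.

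These sizes rest on assumed course and gap lengths and on on-schedule dosing within each course. The number of re-initiated subjects is unknown and may be zero. The primary cutoff is Week 13 of the last subject, and protocol 6.2 calls for at least 12 months of treatment after a confirmed complete response (and/or until progression or unacceptable toxicity). Few complete-response retreatments will therefore precede that cutoff, and the final analysis is the more exposed.

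**What to change.** - Define first dose, last dose and on-treatment period per treatment course in SAP 13.2 and 15.2, each course ending at its own last dose plus the stated tail.
- Report the initial and re-initiated courses separately.
- For totals, sum durations and doses, and compute overall dose intensity as total cumulative dose divided by summed course duration, in cycles. Do not sum dose intensities: two on-schedule courses would give an RDI of 200%.
- Exclude the gap between courses from the dose-delay category.
- State how restart doses are coded in the weekly cohort.
- Reconcile protocol 6.2 with SAP 13.3, so that it is clear for the local-treatment routes whether the interval is a dose delay or a gap between courses. Say also where the protocol 7.1.2 route (progression not confirmed) belongs, since SAP 13.3 does not list it.

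The cost is a paragraph of SAP text, one course variable in the analysis datasets, and a sponsor decision on the reconciliation. The change needs no new data collection.

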15.1 Dose Limiting Toxicity (DLT)

The primary endpoint of the study is:

- Occurrence of DLTs during the DLT observation period. The number and proportion of subjects experiencing DLTs will be reported by dose level based on the DLT Analysis Set (excluding 10 mg/kg once weekly cohort).

Dose limiting toxicity (DLT) refers to relevant toxicity induced by the drug during the first 21 days of treatment; excluding 10 mg/kg once weekly cohort, severity of which is clinically unacceptable, limiting further dose escalation. According to toxicity evaluation criteria in NCI CTCAE V4.03, the observation period for a DLT is the 21-day period after the first administration of avelumab for subjects with data used for implementing the dose-escalation algorithm for dose determination.

DLT data will be captured from the eCRF “ADVERSE EVENTS DETAILS” form.

The Incidence rates of DLT per each dose level during DLT observation will be presented as well as by SOC and PT. DLT summary will be based on DLT set.

15.2 Adverse Events (AE)

An AE is any untoward medical occurrence in a subject or clinical investigation subject administered a pharmaceutical product, which does not necessarily have a causal relationship with this treatment. An AE can therefore be any unfavorable and unintended sign (including an abnormal laboratory finding), symptom, or disease temporally associated with the use of a medicinal product, whether or not considered related to the medicinal product.

If the severity/intensity of a particular AE is not specifically graded by the guidance document, the Investigator is instructed to revert to the general definitions of Grade 1 through Grade 5 and use his or her best medical judgment.

The 5 general grades are:

- Grade 1: Mild
- Grade 2: Moderate
- Grade 3: Severe
- Grade 4: Life-threatening or disabling
- Grade 5: Death related to AE

AEs will be coded using the latest version of Medical Dictionary for Regulatory Activities (MedDRA). The severity of AEs will be graded by the investigator using the NCI-CTCAE version 4.03.

Treatment emergent adverse events (TEAEs) are those events that emerge during treatment having been absent pre-treatment, or worsen relative to the pre-treatment state and with onset dates

occurring within the first dosing day of study dose levels until 30 days after the last dose of study treatment.

All analyses described **Error! Reference source not found.** will be based on TEAEs (started during the on-treatment period) if not otherwise specified. The AE listings will include all AEs (whether treatment-emergent or not). AEs outside the on-treatment period will be flagged in the listings. A separate listing including AEs started after the on-treatment period will also be provided.

- **Related Adverse Events:** adverse events with relationship to study treatment (as recorded on the AE eCRF page, Relationship with study treatment = Related) reported by the investigator and those of unknown relationship (i.e. no answer to the question “Relationship with study treatment”).
- **Serious Adverse Events (SAE):** serious adverse events (as recorded on the AE eCRF page, Serious Adverse Event = Yes).
- **Related SAEs**
- **Adverse Events Leading to Treatment Discontinuation:** adverse events leading to permanent discontinuation of study treatment (as recorded on the AE eCRF page, Action taken with study treatment = Drug withdrawn).
- **Related AE Leading to Treatment Discontinuation**
- **Adverse Events Leading to Death:** adverse event leading to death (as recorded on the AE eCRF page, Outcome = Fatal, as well as AEs of Grade 5).
- **Related AE Leading to Death**
- **Immune Related Adverse Events (irAE):** immune related adverse events are identified via customized MedDRA PT queries and additionally classified by investigator according to case definition (two level approach). Details are included in Appendix 18.2.
- **Infusion Related Reactions (IRR):** IRRs are identified based on a list of MedDRA PTs. The detailed criteria of the timing relationship to infusion are specified in Appendix 18.2.

Incomplete AE-related dates will be handled as follows:

- Incomplete or missing start date:
 - In case the onset date is completely missing or the onset is in the same year (if the onset year is available only) or the onset is in the same month and year (if the day is missing) as start of study treatment, then the onset date will be replaced by the minimum of start of study treatment date and AE resolution date (imputed, if incomplete).
 - In all other cases the missing onset day or onset month will be replaced by 01.
- Incomplete or missing stop date:

- Incomplete stop dates will be replaced by the last day of the month (if day is missing only), if not resulting in a date later than the date of subject's death. In the latter case the date of death will be used to impute the incomplete stop date.
- In all other cases, the incomplete stop date will not be imputed.

AEs will be coded using the latest version of Medical Dictionary for Regulatory Activities (MedDRA). The severity of AEs will be graded by the investigator using the NCI-CTCAE version 4.03.

The AE reporting period for safety surveillance begins when the subject is included in the study (date of first signature of informed consent) and continues for all SAEs and treatment-related non-serious AEs through to the study's Safety Follow-up Phone Call, defined as 90 days (\pm 7 days) after the last administration of avelumab. Any SAE suspected to be related to avelumab must be reported whenever it occurs, irrespective of the time elapsed since the last administration of avelumab.

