#### **7.4.1.3 Definition of the Adverse Event Reporting Period**

The AE reporting period for safety surveillance begins when the subject is included in the study (date of first signature of informed consent) and continues through the 30-days ( $\pm 5$  days) Safety Follow-up Visit. After the Safety Follow-up Visit all SAEs and treatment-related nonserious AEs need to be documented up until the Safety Follow-up Phone Call, which is defined as 90 days ( $\pm 5$  days) after the last administration of avelumab.

Any SAE suspected to be related to avelumab must be reported whenever it occurs, irrespective of the time elapsed since the last administration of avelumab.

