#### Adverse Events

All AEs will be coded according to the Medical Dictionary for Regulatory Activities. Severity of AEs will be graded using the NCI-CTCAE v4.03 toxicity grading scale.

Treatment-emergent AEs are those events with an onset date occurring during the on-treatment period or if the worsening of an event is during the on-treatment period.

The incidence of TEAEs, regardless of attribution and AEs, defined as possibly related to study treatment will be summarized by Preferred Term and System Organ Class, and described in terms of intensity and relationship to study treatment. Adverse events (serious and nonserious) will be considered TEAEs, except for AEs which started prior to the first administration of avelumab (unless a worsening of the event is recorded after the first administration of avelumab, in which case the event will be considered a TEAE). All premature terminations will be summarized by the primary reason for study withdrawal.

Descriptive statistics will be examined for indications of dose-related ADRs.

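### SAP 15.2 ties treatment emergence to the onset date even for events that worsen, so an AE recorded once before the first dose that worsens on avelumab is a TEAE under the protocol but not in the SAP tables

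*SAP*

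**What the plan says.** **Protocol 8.5.3.1 (Adverse Events).** An AE is treatment-emergent if its onset falls in the on-treatment period, "or if the worsening of an event is during the on-treatment period". The same subsection then deals with AEs that began before dosing. They are not TEAEs "unless a worsening of the event is recorded after the first administration of avelumab, in which case the event will be considered a TEAE". The on-treatment period starts at the first administration.

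**Protocol 7.4.1.3.** AE reporting "begins when the subject is included in the study (date of first signature of informed consent"), so AEs with onset before the first dose are collected.

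**SAP 15.2.** TEAEs are events absent before treatment that emerge during it, "or worsen relative to the pre-treatment state and with onset dates" in a stated window. That window, which the SAP applies to the onset and not to the worsening, runs from the first dosing day to 30 days after the last dose. The following paragraph says that the analyses "will be based on TEAEs (started during the on-treatment period) if not otherwise specified". Worsening is not mentioned there.

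**SAP Section 7.** The only declared departure from the protocol's planned analyses concerns biomarkers. The change list for Final 2.0 (SAP Section 3) does not mention the TEAE definition.

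**The concern.** In the protocol, onset and worsening are alternatives. In the SAP, the onset condition is attached to the worsening limb. An AE that opens during screening and becomes more severe on avelumab meets the protocol rule and fails the SAP rule.

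Occurrence of TEAEs and occurrence of treatment-related AEs are secondary endpoints (protocol 8.3.2). SAP 15.2.1 builds the overview and the frequency tables on TEAEs: related, serious, Grade 3 or higher, leading to discontinuation, leading to death. The events at issue are worsenings on drug. Where the two rules differ in this way, the SAP rule can only remove an event from those tables; it cannot add one.

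**Working it through.** The plan states no figure on this point, so the check compares two rules. Let W be the period from first administration to the end of the on-treatment window. The documents also differ on where that window ends, because the protocol stops it the day before subsequent anticancer drug therapy if that is earlier. That difference is set aside here.

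**The rules**

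- Protocol: onset in W, *or* worsening in W.
- SAP: (absent before and emerging, *or* worsening) *and* onset in W. The sentence could also be parsed so that the onset condition attaches only to the worsening limb. On either parsing, a worsened event needs its onset in W.

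**Applied to four kinds of record**

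| Record | Protocol | SAP |
|---|---|---|
| (a) Absent before, onset on treatment | TEAE | TEAE |
| (b) Onset after consent and before first dose, no worsening | not a TEAE | not a TEAE |
| (c) Recorded once, onset after consent and before first dose, worsens on treatment (for example Grade 1 on Day -7, Grade 3 on Day 10) | TEAE | not a TEAE |
| (d) Medical-history condition first reported as an AE when it worsens on treatment, onset entered as the worsening date | TEAE | TEAE |

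The rules differ only in case (c).

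**Can case (c) occur?** AEs are collected from consent, and screening is to be completed within 14 days before the first dose (protocol synopsis, study duration), so there is an interval in which such an AE can open. The SAP's onset-date imputation acts only on missing or partial dates, so it does not move a complete pre-dose onset into W.

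**Does it reach the tables?** That depends on how the AE page records a worsening:

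- A new record with its own onset date: both rules count it, and the tables agree.
- One record carrying dated grade changes or an equivalent flag: the protocol counts it, the SAP does not, and the tables differ.
- One record with a single worst grade and no date of worsening: the SAP excludes it, and the protocol rule cannot be applied without further data.

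Protocol 7.4.1.2 leaves such detail to the eCRF Completion and Monitoring Conventions, which are not part of these documents.

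**Size of one misclassified subject**

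- Planned sizes: 3 (3 mg/kg, if not expanded) + 6 (10 mg/kg every 2 weeks) + 6 (20 mg/kg) + 6 (10 mg/kg weekly) = 21; up to about 24.
- In a cohort of 3: 1/3 = 33.3 percentage points.
- In a cohort of 6: 1/6 = 16.7 percentage points.
- Overall: 1/21 = 4.8 or 1/24 = 4.2 percentage points.

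**The case against.** The strongest reply is that the discrepancy may never reach a table. Protocol 7.4.1.2 has unfavourable changes in the subject's condition recorded as AEs, and protocol 7.4.4 has worsening conditions reported as AEs. If sites open a new record at each worsening, the SAP captures the event. This stands as a limit on the effect. It does not settle the matter, because neither section says that an AE already on file gets a second record and a new onset date. The protocol's own clause on AEs begun before dosing describes a single event that later worsens.

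Four stronger readings are tempting, and the documents do not support them:

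- **The SAP's worsening limb is empty.** It is not. Under protocol 7.4.1.1 a baseline condition is not an AE unless it worsens. Such a condition can enter as an AE with an on-treatment onset and then meets the SAP rule (case d).
- **The events disappear.** They do not. SAP 15.2 lists all AEs, treatment-emergent or not, and flags those outside the on-treatment period. All SAEs are listed, and gradable haematology and biochemistry changes also appear in the baseline-to-worst shift tables (SAP 15.3).
- **Dose escalation is affected.** It is not. DLTs have their own definition (protocol 7.4.1.1) and analysis set (SAP 8.2 and 15.1), and the escalation criteria use DLT counts.
- **The bias can be quantified.** It cannot. The documents give no rate of screening-period AEs and no rate of worsening, so any count would rest on assumptions alone. The number may be zero.

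It is also fair to say that the analyses are descriptive, and that the SAP states it is based on protocol Section 8. That suggests a drafting slip and not a chosen narrower definition, which argues for correcting the wording.

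**Conclusion.** The point holds in a limited form. As written, SAP 15.2 is narrower than protocol 8.5.3.1 for one class of event: an AE recorded once, with onset between consent and first dose, that worsens on avelumab. Such an event leaves the TEAE tables for a secondary endpoint without a declared change, although it remains in the listings.

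The practical effect depends on AE recording conventions that cannot be seen here. If one subject is affected, the row for that term or grade moves by 16.7 points in a cohort of 6 or 33.3 points in a cohort of 3. A summary row moves only if the subject has no other event qualifying for that row; a subject with another TEAE still counts under any TEAE, for example.

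The wording should be corrected before the tables are produced.

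**What to change.** 1. Restate the TEAE definition in SAP 15.2 as in protocol 8.5.3.1: onset in the on-treatment period, or onset before first administration with a worsening recorded in the on-treatment period.
2. In the next paragraph of SAP 15.2, change the bracketed restriction to *started or worsened during the on-treatment period*.
3. Check the eCRF completion conventions, then derive worsening from whatever the AE page captures (dated grade changes or new records). State which date and grade are used for a worsened pre-dose AE.
4. Add a rule comparing a single record's grade with the grade at first dose only if that grade is available; the documents do not show that it is.

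The cost is two wording changes, one derivation and the check of the conventions. If sites already open a new record at each worsening, no result changes. If the page holds only one undated worst grade, the wording change alone will not recover these events, and the SAP should say so.
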